### 6.2 XPO1 induction/inhibition

Whole blood (2 tubes X 2.5 mL) will be obtained to assess XPO1 induction/inhibition in leukocytes prior to the first dose of selinexor and 4 hours (+/- 1) hours post the first dose of selinexor on cycle 1 day 1 only, by quantitative real time polymerase chain reaction (qRT-PCR). Karyopharm Therapeutics will be responsible for this testing. Karyopharm will also analyze a panel of additional genes as well as microRNA expression on the blood samples from these time points.

A Karyopharm Therapeutics laboratory manual (Appendix F) and supplies has been provided to facilitate testing. Sample collection and shipment details will be included in the laboratory manual.

### **6.3 Plasma protein/cytokine analysis**

Plasma samples (2 ml) will be collected prior to the first dose of selinexor and 4 hours (+/-1) hours post the first dose of selinexor on cycle 1 day 1 only, and will be analyzed for plasma proteins/cytokine concentrations. Karyopharm Therapeutics will be responsible for this testing. A Karyopharm Therapeutics laboratory manual and supplies has been provided to the site in order to facilitate testing. Sample collection and shipment details will be included in the lab manual.

## **7.0 PATIENT EVALUATION**

Every effort will be made to adhere to the schedule of events and all protocol requirements. Variations in schedule of events and other protocol requirements that do not affect the rights and safety of the patient will not be considered as deviations. Such variations may include laboratory assessments completed outside of schedule, occasional missed required research samples such correlative assays.

### **7.1 Pre-Treatment Evaluation**

All pretreatment studies should be obtained within 14 days from time of first dose of the study drug administration, unless otherwise specified:

- 7.1.1 A complete history and physical, concomitant medications and performance status.
- 7.1.2 CBC, platelet count, hemoglobin, differential (differential can be omitted if WBC is  $\leq 0.5 \times 10^9/L$ ).
- 7.1.3 Creatinine, BUN, direct bilirubin, total bilirubin, AST, ALT.
- 7.1.4 Serum or urine pregnancy test in females of childbearing potential, should be performed within 72 hours before the initiation of therapy.
- 7.1.5 Bone marrow aspirate within the last 7 days preceding study initiation.
- 7.1.6 Evaluation of FLT3-ITD and -D835, NPM1, IDH1 & 2 should have been done within 60 days preceding study initiation.
- 7.1.7 12-lead EKG and ECHO and/or MUGA.
- 7.1.8 A baseline neurological examination will be documented for all patients within the last 7 days preceding study initiation. MRI Brain will be performed at the discretion of the treating physician and/or the PI if clinically indicated.

7.1.9 A baseline full Ophthalmological and Visual Acuity Examination, including slit lamp examination and anterior segment photographs for cataracts or other abnormalities must be performed at screening and must be document for all patients. Follow-up ophthalmologic evaluations will be performed if clinically indicated during the study.

7.1.10 Pretreatment optional correlative studies (see section 6.0)

Peripheral blood (up to 35 cc) – (1) Flow cytometry for CD34/annexinV/CMXRos, (2) Vectra, (3) RPPA, (4) RT-PCR for selected genes, and (5) XPO1 induction/inhibition in leukocytes and plasma protein/cytokine analysis in the blood prior to first dose of selinexor at baseline (Cycle 1 Day 1)

Bone marrow samples (up to 10 cc): (1) Flow cytometry for CD34/annexinV/CMXRos, (2) Vectra, (3) RPPA in the bone marrow at baseline, and (4) RT-PCR for selected genes (within the last 7 days preceding study initiation)

## 7.2 Evaluation During Treatment

7.2.1 Physical exam on day 1 of each cycle ( $\pm$  1 days) for the first 4 cycles, then every 1-2 cycles.

7.2.2 CBC, platelet count, hemoglobin, differential at least once weekly for the first 3 cycles, then every 2-4 weeks (differential can be omitted if WBC is  $\leq 0.5 \times 10^9/L$ ). Outside labs may be used, but the PI/Treating physician must review all protocol specific outside lab results and determine the clinical significance of abnormal values then sign/date the results or dictate this process in the medical record.

7.2.3 Creatinine, BUN, total bilirubin, ALT, AST weekly ( $\pm 4$  days) for the first 3 cycles, then every 2-4 weeks.

7.2.4 Laboratory tests can be ordered more frequently if mandated by development of peripheral blast/blood counts or electrolyte/liver function test abnormalities.

7.2.5 Bone marrow aspiration for differential and PCR for FLT3 on day 28 ( $\pm 7$  days) of cycle 1, day 28 of cycle 3 ( $\pm 7$  days), then every 1-3 cycles. Bone marrow tests can be ordered more frequently if mandated by development of peripheral blood counts. No repeat bone marrow is necessary if nonresponse or progressive disease can be unequivocally diagnosed from peripheral blood tests or, in patients with a WBC  $< 0.3$  if the bone marrow test is considered noncontributory by the investigator at any time point.

- 7.2.6 Concomitant medication data will not be collected or entered into the case report form (PDMS is the case report form for this study). Concomitant medication data will not be collected or entered into the case report form except for concomitant hydroxyurea if administered during the first cycle; however, the subject's medication record will contain a list of concomitant medications.
- 7.2.7 12-lead EKG will be performed on day 1 ( $\pm 1$  day) of each cycle for the first 4 cycles, then every 1-3 cycles
- 7.2.8 Peripheral blood (up to 35 cc each time) and bone marrow (up to 10 cc each time) for pharmacodynamic studies (Optional) as defined in section 6.2 on
- **Peripheral blood:**
  - Prior to first dose of selinexor at baseline (Cycle 1 Day 1) as per section 7.1.10.
  - Cycle 1 Day 1: 4 (+/- 1) hours after the first dose of selinexor to evaluate (1) XPO1 induction/inhibition in leukocytes and (2) plasma protein/cytokine analysis
  - Cycle 1 Day 2: 24 (+/-4) hours after first dose of selinexor for evaluation of (1) Flow cytometry for CD34/annexin V/CMXRos, (2) Vectra, (3) RPPA, and (4) RT-PCR for selected genes
  - Cycle 1 Day 28 (+/- 7 days): for evaluation of (1) Flow cytometry for CD34/annexinV/CMXRos, (2) Vectra, (3) RPPA, and (4) RT-PCR for selected genes
  - At progression/relapse (if sample available): for evaluation of (1) Flow cytometry for CD34/annexinV/CMXRos, (2) Vectra, (3) RPPA, and (4) RT-PCR for selected genes
  - **Bone marrow samples:**
  - At screening (within the last 7 days preceding study initiation) as per section 7.1.10.
  - At the time of disease assessment on day 28 (+/- 7 days): for evaluation of (1) Flow cytometry for CD34/annexinV/CMXRos, (2) Vectra, (3) RPPA, and (4) RT-PCR for selected genes
  - At progression/relapse (if sample available): for evaluation of (1) Flow cytometry for CD34/annexinV/CMXRos, (2) Vectra, (3) RPPA, and (4) RT-PCR for selected genes
  - Missed samples for correlative studies will not constitute protocol deviations. These studies are optional on this protocol.

7.2.9 All treatment prescriptions for sorafenib and selinexor must be written by the patient's attending physician at MDACC or the PI of the study. We do not intend for the subjects to receive prescriptions for sorafenib or selinexor at an outside physician's office. During the first cycle all the protocol required laboratory evaluations will be done at MDACC. Subsequently, the patient may have the laboratory work done at a local clinic and the results reported to the research nurse for the study. The laboratory work done at the local clinic will be forwarded to the patient's attending physician at MDACC or PI of the study, who will sign off on the labs to verify that the results have been reviewed.

### **Outside Physician Participation During Treatment**

1. MDACC Physician communications with the outside physician is required prior to the patient returning to the local physician. This will be documented in the patient record.
2. A letter to the local physician outlining the patient's participation in a clinical trial will request local physician agreement to supervise the patient's care (Appendix G).
3. Protocol required evaluations outside MDACC will be documented by telephone, fax or e-mail. The PI/treating physician must review the labs, determine clinical significance and sign and date the report.
4. A copy of the informed consent, protocol abstract, treatment schema and evaluation during treatment will be provided to the local physician.
5. Documentation to be provided by the local physician will include progress notes, reports of protocol required laboratory and diagnostic studies and documentation of any hospitalizations.
6. The home physician will be requested to report to the MDACC physician investigator all life threatening events within 24 hours of documented occurrence.
7. All follow-up visits will be performed at MDACC.
8. Changes in drug dose and/or schedule must be discussed with and approved by the MDACC physician investigator, or their representative prior to initiation, and will be documented in the patient record.

- 7.2.10 For patients that remain on study with no significant toxicity for more than 6 months, subsequent evaluations during study may be modified after discussion with the PI. These include a decrease in frequency of bone marrow aspirations to every 6-12 months (or as clinically indicated) and other laboratory tests to once every cycle.
- 7.2.11 Pregnancy test (urine or serum) in females of childbearing potential every 3 months ( $\pm 2$  weeks).
- 7.2.12 Patients with an objective response will be followed for survival at MD Anderson Cancer Center (MDACC) every 3 to 6 months after the end of treatment visit for up to 5 years after completion of active treatment. If the patient is unable to return to MDACC the follow-up visits may be conducted via telephone.

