#### **Phase II**

1. To determine the PR, marrow clearance rate, bone marrow blast reduction  $\geq 50\%$  within 3 months of treatment initiation in FLT3-ITD and –D835 mutated patients with relapsed/ refractory AML.
2. To determine the DOR, EFS, OS, and number of patients bridged to HSCT and median duration to HSCT from the initiation of the combination of selinexor with sorafenib in FLT3-ITD and –D835 mutated patients with relapsed/ refractory AML.
3. To determine the safety of the combination of selinexor with sorafenib in FLT3-ITD and –D835 mutated patients with relapsed/ refractory AML.

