## **8.0 CRITERIA FOR RESPONSE**

Response criteria will be modified from the International Working Group for AML. Responders are patients who obtain a Composite Complete Remission Rate (CRc) with or without cytogenetic response, hematologic improvements, and morphologic leukemia-free state. CRc rate is defined as the confirmed remission rate of all complete and incomplete CRs (i.e., CR+ CRp + CRi).

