### **9.1.4 Follow-Up at Treatment Discontinuation or Early Withdrawal**

Patients who discontinue treatment for any reason should complete end-of-treatment procedures when possible. End of treatment procedures will include a physical examination, CBC with differential and platelets and a limited chemistry profile (total bilirubin, serum creatinine, SGPT or SGOT). A bone marrow aspiration may be recommended only if non-response or progressive disease cannot be unequivocally diagnosed from peripheral blood. Although treatment will be discontinued at that time, all patients who do not withdraw consent for follow-up, die, or become lost to follow-up, will remain on study for follow-up evaluations. Subject will be followed for toxicity for at least 30 days after the last protocol treatment. The 30-day (+/-7 days) follow-up visit will be scheduled as a clinic visits for clinical evaluation and physical examinations. If the patient cannot make it to the MDACC clinic for this visit, the required follow up treatment procedures may be done with a local physician and the records forwarded to MDACC. The research nurse will contact the patient by telephone and get a verbal assessment of the patient's condition. The phone conversation will then be documented in the patient's charts.

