### 11.3 Statistical Analysis Plan

All patients who received any dose of the study agent will be included in the analysis for efficacy and safety. Demographic/clinical characteristics (including duration of response) and safety data of the patients will be summarized using descriptive statistics such as mean, standard deviation, median and range. For the primary efficacy analysis, we will estimate the ORR for the combination treatment, along with the 95% confidence interval. In addition, we will estimate composite CRc rate, partial response and marrow clearance rate within 3 months by FLT3 mutation. Patients who drop out of the study before completing all the cycles will be treated as “failures” for the primary analysis. ORR during the study period will also be presented with the 95% confidence interval. The association between ORR and patient’s clinical characteristics will be examined by Wilcoxon’s rank sum test or Fisher’s exact test, as appropriate. Toxicity type, severity and attribution will be summarized for each patient using frequency tables.

The distribution of time-to-event endpoints (DFS and OS) including overall survival and progression free survival will be estimated using the method of Kaplan and Meier. Comparisons of time-to-event endpoints by important subgroups will be made using the log-rank tests. Paired t-tests will be used to determine the immunological and molecular changes in the peripheral blood and bone marrow from baseline to the time of response, and to the time of disease progression.

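### Survival follow-up is scheduled only for objective responders, so OS could read too high, and Section 11.3 gives DOR and EFS no time-to-event analysis

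*Combined protocol and SAP*

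**What the plan says.** - **Objectives (Section 1.2).** The phase II secondary objectives include "To determine the DOR, EFS, OS, and number of patients bridged to HSCT". Phase I has the same endpoints. Neither list restricts them to responders.
- **Analysis population (Section 11.3).** "All patients who received any dose of the study agent will be included in the analysis for efficacy and safety".
- **Survival follow-up (Section 7.2.12).** "Patients with an objective response will be followed for survival", every 3 to 6 months for up to 5 years, with telephone contact allowed. No other section schedules survival follow-up.
- **After discontinuation (Section 9.1.4).** "all patients who do not withdraw consent for follow-up, die, or become lost to follow-up, will remain on study for follow-up evaluations". What those evaluations are, how often they occur and for how long is not stated. The only timed element is "Subject will be followed for toxicity for at least 30 days after the last protocol treatment", with a 30-day visit.
- **Who is a responder (Section 8.0).** "Responders are patients who obtain a Composite Complete Remission Rate (CRc) with or without cytogenetic response", and the sentence goes on to mention hematologic improvement and leukemia-free marrow. The term objective response is not defined.
- **Time-to-event methods (Section 11.3).** The Kaplan-Meier sentence covers "The distribution of time-to-event endpoints (DFS and OS) including overall survival and progression free survival". DOR appears in a different sentence, among the characteristics to be described: "including duration of response) and safety data of the patients will be summarized using descriptive statistics such as mean, standard deviation, median and range".

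**The concern.** The survival schedule covers a group chosen by outcome, while the analysis covers everyone. If staff follow 7.2.12 as written, non-responders have no scheduled contact after the 30-day visit and are censored there if still alive. Responders stay under observation for years. Censoring then depends on prognosis, which Kaplan-Meier does not allow for. The later part of the OS curve comes to rest mainly on responders, and OS reads too high. EFS is exposed to the same gap for deaths after treatment ends.

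Two further gaps lie in Section 11.3. DOR is a time-to-event quantity, but it is given summaries for complete data and no rule for responses still ongoing at analysis. If those enter the mean as though they had ended, DOR is understated. And EFS, an objective, is neither defined nor named in the Kaplan-Meier sentence, while DFS and PFS are named there and are not objectives.

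**Working it through.** The documents give no OS, EFS or DOR rate for this trial, so there is no planned figure to reproduce.

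**1. How many patients are outside the schedule.** Inputs are 20 patients per cohort and the CRc rates in Section 11.2: target 35% and historical 20% for the FLT3-inhibitor-naive cohort, target 20% and historical 10% for the FLT3-inhibitor-failure cohort. Take objective response to mean CRc.

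- Target: 20 × (1 − 0.35) = 13 and 20 × (1 − 0.20) = 16, together 29 of 40.
- Historical: 20 × (1 − 0.20) = 16 and 20 × (1 − 0.10) = 18, together 34 of 40.
- A wider reading, at the 40-50% marrow response that Section 2.1 cites for FLT3 inhibitors: 40 × 0.60 = 24 to 40 × 0.50 = 20 of 40.

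**2. Size of the OS bias.** All survival inputs here are assumptions.

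- Responder share p: 10, 20 or 35%.
- Median OS: 9 or 12 months in responders; 3, 4 or 5 months in non-responders.
- Median time on drug in non-responders d: 1, 2, 3 or 6 months, with last contact one month after the last dose.
- f: the share of non-responders whose vital status is found anyway.

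Survival and time on drug are exponential. With hazards λ = ln 2 / median, true survival is S(t) = p·S_R(t) + (1 − p)·S_N(t). Non-responders remain under observation with probability G(t) = 1 before month 1 and f + (1 − f)·2^(−(t−1)/d) afterwards. In large samples Kaplan-Meier converges to exp(−∫h), where

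h = [p·S_R·λ_R + (1 − p)·S_N·G·λ_N] / [p·S_R + (1 − p)·S_N·G].

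Central case (p = 20%, medians 10 and 4 months, d = 3): the true 12-month OS is 0.20 × 2^(−12/10) + 0.80 × 2^(−12/4) = 0.087 + 0.100 = 18.7%. Kaplan-Meier reads 25.6% at f = 0, 20.8% at f = 0.5 and 19.4% at f = 0.8.

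Excess in 12-month OS over the 3 × 2 × 3 × 4 = 72 scenarios, in percentage points:

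| Vital status found (f) | Median time on drug | Excess |
|---|---|---|
| 0 | 1 month | 8.9 to 17.5 |
| 0 | 2 months | 6.1 to 11.8 |
| 0 | 3 months | 3.9 to 8.6 |
| 0 | 6 months | 1.6 to 4.9 |
| 0.5 | all | 0.5 to 5.2 |
| 0.8 | all | 0.2 to 1.7 |

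At f = 0 the 6-month excess is 0.5 to 12.2 points and median OS is overstated by 0.03 to 2.7 months.

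A separate simulation used a fixed time on treatment of 1 to 3 months, responder shares of 10-50%, and median OS of 3-6 months in non-responders and 9-12 months in responders. It gave an excess of about 7 to 24 points, upward in every scenario.

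**3. DOR.** Section 2.1 puts response to FLT3 inhibitors at 3-6 months; read these as medians. Assume exponential DOR, uniform accrual over 18 months, response at 2 months, no transplant, and analysis x months after the last patient enters. With mean τ = median / ln 2 and available follow-up A, the raw mean divided by the true mean is 1 − E[exp(−A/τ)], and E[exp(−A/τ)] is the share of responses still ongoing.

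| Median DOR | x = 3 | x = 6 | x = 12 |
|---|---|---|---|
| 3 months | 0.81 | 0.91 | 0.98 |
| 6 months | 0.63 | 0.73 | 0.87 |

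So about 2 to 37% of responses are ongoing, and the raw mean is about 63 to 98% of the true mean.

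**The case against.** The strongest reply is that Section 9.1.4 already retains everyone. It lists death, loss to follow-up and withdrawal of consent as the exits, so retention is limited neither to responders nor to 30 days, and nothing says non-responders are censored at that visit. This stands in part: the plan does not state an intention to drop non-responders, and the bias disappears if 9.1.4 is applied as survival follow-up for all. But 9.1.4 does not mention survival and gives no interval or duration, and the one section that does schedule survival names a narrower group.

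The sizes rest on assumptions. For one identical case (20% responders, medians 12 and 4 months, 2 months on drug) the excess is about 18 points with fixed time on drug and about 11 with exponential time. That is fair, and the figures show direction and plausible range only. The count of 29 to 34 of 40 depends on reading objective response as CRc; the wider reading gives 20 to 24. If sites hear mainly of deaths, the upward bias shrinks faster and could turn slightly downward.

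For DOR, the listed statistics are examples, and nothing says ongoing responses count as completed. With analysis 24 to 36 months after the last patient, the raw mean is 97 to 100% of the true mean.

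Finally, these are secondary endpoints with no decision rule, and 20 patients give wide intervals: 1.96 × √(0.187 × 0.813 / 20) = 17 points either side of 18.7%. That limits the consequence, but a wide interval does not remove a bias. The DFS/PFS/EFS mismatch on its own would be an editorial point.

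**Conclusion.** The concern holds. Sections 7.2.12 and 9.1.4 are not reconciled, and following 7.2.12 literally would censor OS by prognosis. Under the assumed inputs, 12-month OS would read 1.6 to 17.5 points too high with no tracing of non-responders (central case 25.6% against 18.7%), 0.5 to 5.2 points with half traced, and 0.2 to 1.7 points with 80% traced. These partial figures take tracing to be unrelated to outcome. DOR lacks a censoring rule, and its raw mean could fall to about 63% of the true value if the analysis comes early and ongoing responses are counted as finished. EFS has no definition and no named analysis. Confidence in the direction is good; confidence in the size is limited, because the documents give no survival or time-on-treatment figures. The primary CRc endpoint and the stopping rules are untouched, so this is a recommended amendment and not an obstacle to the main analysis.

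**What to change.** 1. In 7.2.12, apply the existing survival schedule to every treated patient who has not withdrawn consent to follow-up. Keep its interval, its starting point after the end-of-treatment visit, its five-year limit counted from the end of active treatment, and the telephone option. Refer to it from 9.1.4.
2. In 11.3, estimate DOR by Kaplan-Meier from first response, censoring patients without relapse at their last disease assessment. State how death without relapse and HSCT are handled.
3. Define EFS (start, events, censoring) and name it in the Kaplan-Meier sentence in place of DFS and PFS. If DFS or PFS is wanted, add it to the objectives with a definition.
4. If objective response is used elsewhere to select patients, define it in Section 8.

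The cost is a short wording amendment plus periodic telephone or record checks for non-responders, among at most 52 patients. Vital status not collected at the time may be hard to recover later.

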## **8.0 CRITERIA FOR RESPONSE**

Response criteria will be modified from the International Working Group for AML. Responders are patients who obtain a Composite Complete Remission Rate (CRc) with or without cytogenetic response, hematologic improvements, and morphologic leukemia-free state. CRc rate is defined as the confirmed remission rate of all complete and incomplete CRs (i.e., CR+ CRp + CRi).

### **8.1 Complete Remission (CR)**

For patients to be classified as being in CR, they must have bone marrow regenerating normal hematopoietic cells and achieve a morphologic leukemia-free state and must have an ANC  $> 1 \times 10^9/L$  and platelet count  $\geq 100 \times 10^9/L$ , and normal marrow differential with  $< 5\%$  blasts, and patients will be red blood cell (RBC) and platelet transfusion independent (defined as 4 weeks without RBC transfusion and 1 week without platelet transfusion). There should be no evidence of extramedullary leukemia.

